### 8.5.2 Secondary objectives

- Compare the short-term clinical effectiveness of laminectomy and laminectomy and fusion at 12 months post-surgery
- Compare pain, quality of life, surgical complications, and radiological measures between the two groups
- Undertake a detailed economic analysis
- Undertake a predefined secondary analysis of:
  - Number of levels treated
  - Presence / Amount of movement pre-operatively (>1mm subluxation on flexion/extension X-Ray)
  - Presence of auto-fusion at 1 or more cervical level pre-operatively (radiological evidence of spontaneous fusion between two adjacent vertebrae)
  - Presence of Kyphosis (C2-C7 Cobb Angle <0°)
  - Presence of Cervical Ossification of Posterior Longitudinal Ligament
  - Previous Cervical Spine Surgery
  - Age
- Undertake a predefined subgroup analysis of
  - Participants satisfying the criteria of modified K Line Negative, on pre-operative imaging

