#### 11.3.1 Screening Assessments

Potentially eligible patients with DCM will be approached by a delegated member of the local trial team and given a PIS to read in their own time. Patients will be offered the opportunity to ask questions, or advised to get in touch in order to address any questions that they may have on the contents of the PIS. If they decide to participate in the trial, they will undergo a screening assessment to confirm their eligibility for the trial as per inclusion/exclusion criteria described in section 9.1 and 9.2.

Screening assessments to establish eligibility will include:

- Age
- mJOA
- Planned Surgical Intervention
- DCM characteristics
  - Symptoms
  - Length of DCM symptoms
  - MRI image findings

- Number of cervical spine levels for treatment
- Neurological examination

*Estimated time: <30minutes.*

An anonymised record of the patients approached along with the numbers of, and reasons for, screen failures and refusal of consent will be kept at each site on a screening log and reported to the Trial Co-ordinating Centre on a monthly basis. This information will be used to identify any barriers to recruitment and allow improvement measures to be identified and implemented in a timely manner.

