### 11.3.2 Participant Registration/Randomisation

Following screening, eligible subjects will be randomised to either laminectomy and or laminectomy and fusion. They will then be given a unique trial ID number.

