### **11.5.2 Intra-Operative Assessments**

- Operation title
- Cervical Levels treated
- American Society Anaesthesiology (ASA) grade
- Operation Duration
- Estimated Blood Loss
- Intra-operative complications
- Use of
  - Intra-operative Navigation
  - Intra-operative Neuromonitoring (neurophysiology)
- Nature of Inserted Metalwork, if applicable (number / brand)
- Use of synthetic products to support fusion, e.g. Actifuse, Baxter.

*Estimated time: 5minutes.*

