## 11.6 Schedule of Assessments

\* Optional

§ Performed by Significant Other, with their consent, and optional

Centralised

Assessment	Screening	Randomisation	Pre-operative baseline	Surgery	Post-operatively / Discharge	6 months post operatively (±21 days)	12 months post operatively (±21 days)	24 months post operatively (±21 days)
Informed consent	X							
Age	X							
Gender			X					
Medical History			X					
Medication History/Review			X		X	X	X	X
Charleston Comorbidity Index			X					
DCM characteristics	X		X					
Neurological examination	X							
Myelopathy.org symptom inventory [MOSI]			X			X	X	X
Smoking status			X					
Psychiatric comorbidities			X					
Impaired gait			X					
Randomisation		X						
Weight			X					
mJOA	X		X		X	X	X	X
SF36v2			X		X	X	X	X
EQ5D-5L			X		X	X	X	X
NDI			X		X	X	X	X
BPI			X		X	X	X	X
DN4*			X		X	X	X	X
Michigan Body Map*			X		X	X	X	X
Healthcare Resource Usage Questionnaire			X			X	X	X
PHQ9*			X					
GAD7*			X					
Complications				X	X	X	X	X
Cervical X-Rays			X		X*	X	X*	X
Operation title				X				
ASA grade				X				

Cervical levels treated				X				
Operation Duration				X				
Intra-Operative Blood Loss				X				
Adverse event assessments				X	X	X	X	X
Treatment details (e.g. procedure, intraoperative adverse events, use of navigation and neuromonitoring; type of metalwork and synthetic products used)				X				
Length of stay and Level of Care				X				
MRI Cervical Spine*							X	
MoveMed*			X	X	X	X	X	X
Carer Quality of Life§			X		X	X	X	X

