## 15 **Statistics**

### 15.1 **Statistical methods**

The primary objective will be evaluated using a two-sided t-test at a 5% significance level. The trial is powered to detect a 1-point difference in the mJOA scale between arms.

The ordering of subsequent endpoints for formal hypothesis testing will be:

1. BPI Pain
2. Neck Disability Index
3. PCS component of the SF-36
4. MCS component of the SF-36
5. mJOA (Upper Limb, Motor Score)
6. mJOA (Lower Limb, Motor Score)

A range of MCID for these endpoints have been proposed using a range of methods. As secondary endpoints the trial is not implicitly powered to detect a specific difference, and instead analysis will estimate the difference. However, in order to recognise what is considered meaningful in advance, the following MCID are agreed based on the available literature; BPI 20mm, NDI 8 points, SF36 PCS 5 points, MCS SF36 4 points, mJOA Subdomain scores 1 point.

A descriptive analysis of the following secondary outcome measures will be provided:

- SF36v2 (Quality of life) Score
- EQ5D-5L
- Neck Disability Index (NDI)
- Brief Pain Inventory (BPI)
- Douleur Neuropathique 4(DN4)
- Michigan Body Map (Pain Location)
- Complications (including surgical site infection, wound breakdown, instrument failure)
- Adverse Events

- Cervical X-Rays (Deformity, Fusion, Movement)
- Neurological examination
- Myelopathy.org Symptom Inventory

A predefined subgroup analysis of the following variables will take place:

- Number of levels treated
- Presence / Amount of movement pre-operatively (>1mm subluxation on flexion/extension X-Ray)
- Presence of auto-fusion at 1 or more cervical level pre-operatively (radiological evidence of spontaneous fusion between two adjacent vertebrae)
- Presence of Kyphosis (C2-C7 Cobb Angle <0°)
- Presence of Cervical Ossification of Posterior Longitudinal Ligament
- Previous Cervical Spine Surgery
- Age

The following baseline covariates, in addition to the baseline value of the endpoint, will be used to adjust all comparisons:

- Time to onset
- Smoking status (yes/no)
- Age
- Psychiatric comorbidities (yes/no)
- Impaired Gait (yes/no)

A detailed statistical analysis plan will be produced before the final data base lock.

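### The levels subgroup should use the number planned at screening, because the number treated is recorded at surgery after allocation and can depend on the arm

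*Protocol*

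**What the plan says.** Section 15.1 announces "A predefined subgroup analysis of the following variables will take place" and puts "Number of levels treated" first of seven. Section 8.5.2 carries the same seven variables. Neither section gives a source, time point or cut-point for the number of levels. The movement and auto-fusion items in the same list are explicitly pre-operative; the levels item is not.

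Two data items could supply the variable:

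- At surgery: "Cervical Levels treated" is in the intra-operative list (11.5.2). In the schedule (11.6), "Cervical levels treated" has one mark, in the surgery column.
- At screening: "Number of cervical spine levels for treatment" is in the screening assessments (11.3.1) and in the synopsis (section 4).

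The order of events is fixed in 11.3.2: "Following screening, eligible subjects will be randomised to either laminectomy and or laminectomy and fusion". Surgery comes later, after an average wait of 79 days (8.4). Section 9.4 says that clinical teams, patients and carers are not blinded.

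On labelling, 8.5.2 puts the seven variables under "Undertake a predefined secondary analysis of". Its one subgroup analysis is of "Participants satisfying the criteria of modified K Line Negative, on pre-operative imaging". Section 15.1 calls the seven variables subgroups and does not mention K-line.

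**The concern.** A subgroup comparison keeps the protection of randomisation only if the arm cannot influence who belongs to the subgroup. The wording in 15.1 points to a variable settled in theatre by people who know the arm. Nothing in the protocol fixes the levels before allocation or requires the operated levels to match the plan. If surgeons treat a different number of levels when they also fuse, patients change stratum in one arm only, and an apparent difference between strata can appear or be hidden.

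This subgroup is likely to be read closely. Section 6.1 says that instability and deformity become more likely and larger as more consecutive levels are operated on, and gives this as the reason some surgeons stabilise the spine. The definition also fits poorly with 15.5, which groups patients as randomised whatever happens later: sorting them by what was done at surgery brings later decisions back in.

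**Working it through.** **1. When each candidate is recorded**

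| Step | Source | Arm known to the team? |
|---|---|---|
| Levels for treatment recorded at screening | 11.3.1, synopsis | No |
| Randomisation | 11.3.2 | Allocated here |
| Average wait of 79 days | 8.4 | Yes (9.4) |
| Levels treated recorded at surgery | 11.5.2, 11.6 | Yes (9.4) |

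The number of levels is not a stratification factor (9.3 uses mJOA, age and time to onset). Even so, randomisation balances the screening count in expectation. It gives no such guarantee for the surgical count.

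**2. The plan's own figure**

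The plan states no figure for this subgroup. Its sample size reproduces: with difference 1, SD 2.89, two-sided 5% and 90% power, a t-test needs 176.5, so 177 per arm and 354 in total. 354/0.9 = 393.3, which rounds up to 394. Evaluable patients per arm are 394 × 0.9/2 = 177.3. Redefining the subgroup changes none of this.

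**3. Illustration of the bias (assumed inputs)**

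Assume that half of each arm is planned for many levels (mean mJOA 13.5) and half for few (mean 14.5), with no treatment effect. Let a fraction m of the few-level patients in the fusion arm, chosen at random, be treated at enough levels to be counted as many. Then:

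fusion mean in the many-level stratum = (0.50 × 13.5 + 0.50m × 14.5)/(0.50 + 0.50m)

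The laminectomy mean there stays at 13.5, so the spurious difference is m/(1 + m):

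| m | Spurious difference, many levels |
|---|---|
| 0% | 0 |
| 5% | 0.05 |
| 10% | 0.09 |
| 20% | 0.17 |
| 30% | (6.75 + 2.175)/0.65 − 13.5 = 0.23 |

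In the few-level stratum both arms keep a mean of 14.5, so the spurious interaction equals the figure shown.

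**4. Size against noise**

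At m = 30% with 177 per arm, laminectomy has 88.5 and 88.5 patients in the two strata, and fusion has 61.95 few and 115.05 many. The interaction SE is 2.89 × √(1/88.5 + 1/88.5 + 1/61.95 + 1/115.05) = 0.63. The bias is 0.23/0.63 = 0.37 SE, and a nominal 5% interaction test would reject in about 6.6% of trials.

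**5. A second set of assumptions**

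A simulation with no treatment effect used planned levels of 2, 3, 4 and 5 in 25, 30, 30 and 15% of patients, a total SD of 2.89, and mJOA falling by 0.5 or 1.0 point per planned level. One level was added in 0 to 30% of the fusion arm, either at random or only in patients with a worse unmeasured prognosis. The cut was at most 3 against at least 4 levels.

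- Grouped by planned levels: within-stratum differences of 0.00 (simulation error about ±0.01).
- Grouped by levels treated: within-stratum differences up to 0.25, and interactions from about −0.22 to +0.14.

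The sign depends on which patients have a level added, so the direction cannot be known in advance.

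**The case against.** The strongest reply is that nothing shows the problem will occur. Sections 10.1.1 and 10.1.2 describe exposure and laminectomy in near-identical terms for both arms; fusion adds an instrumentation step. Patients enter already scheduled for surgery on two or more consecutive laminae (9.1), so the extent is at least partly planned beforehand. If treated means decompressed, screws placed beyond the laminectomy move no one between strata, and metalwork is a separate item in 11.5.2. This stands. A reader might infer that the subgroup effects are confounded as a matter of fact, or that fusion covers more levels. The documents support neither; they support only that bias is possible.

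The illustration uses invented means and migration rates. That also stands, which is why a range is given. In addition, 15.1 adjusts all comparisons for baseline covariates, which would shrink whatever part of the difference between strata baseline severity explains.

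The statistical analysis plan could choose the screening count, and the form of the interaction model belongs there. This only partly answers the point. The protocol's wording names levels treated while neighbouring items say pre-operative, so a plan that follows it would inherit the problem. Section 15.1 requires that plan only before final database lock, when the operated levels will already have been recorded.

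On K-line, a reader might infer from 8.5.2 that only K-line-negative patients will be analysed, with no comparison against the rest. The text does not say so. What stands is the mismatch between the two lists.

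**Conclusion.** The point holds as a weakness in how one subgroup is defined. The named variable matches an item recorded after randomisation by an unblinded team, although a count made before randomisation is already listed. Any bias depends on levels treated differing by arm, for which the documents give no rate. Under the stated assumptions it runs from 0 to 0.23 mJOA points in one stratum, and to about 0.25 in the simulation. That is modest beside the 1-point target and well inside the noise of a subgroup contrast.

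It would be wrong to infer that the main result is at risk: the primary comparison, the sample size and the ordered secondary endpoints do not use this variable. The change is worth making because it removes an avoidable bias at almost no cost.

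The differing labels in 8.5.2 and 15.1, and the absence of modified K-line from 15.1, are a separate inconsistency about which subgroups are predefined.

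**What to change.** - In 8.5.2 and 15.1, define the subgroup as the number of cervical spine levels planned for treatment, as recorded at screening before randomisation (11.3.1).
- Confirm that this item captures the planned extent of the operation. The synopsis nests it under MRI findings and 11.6 gives it no row of its own. If it records only imaging findings, the screening form needs a clearer label or an added field.
- Report levels actually treated by arm, as a description of the surgery only.
- Separately, make 8.5.2 and 15.1 agree on which analyses are the predefined subgroups, and state in both whether modified K-line is one of them.

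If the screening item already holds the planned extent, the cost is wording alone, with no new data and no change to the sample size. If it does not, the cost is one field at screening, and for patients already randomised the planned extent would have to come from records dated before allocation.

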### 9.3 Treatment Assignment and Randomisation Number

An online randomisation system will be used to assign participants in a 1:1 ratio to treatment with either laminectomy alone or laminectomy and fusion. Stratified blocked randomisation will be used stratifying by baseline mJOA (<12 vs >=12), age (<60 years vs >=60 years) and time to onset (>6 months vs <=6 months); random block size will be used.

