### **15.3 Number of Participants to be enrolled**

POLYFIX DCM plans to include 394 participants in total. The pilot phase aims to assess at least 40 participants.

The minimum clinically important difference (MCID) for the mJOA is estimated to be between 1 and 2 points. As the mJOA is demonstrated to improve greater than the MCID with surgery (including laminectomy or laminectomy with fusion) alone, with the amount of change linked to the pre-operative baseline. Consequently, in consensus with patients, we have determined a MCID for the mJOA of 1 point for additional gains. This is in keeping with the trial design of recent DCM RCTs, CSM Protect NCT01257828 and RECEDE-Myelopathy (EducaCT number: 2017-004856-41). This has been modelled to ensure statistical power across all baseline scenarios.

On this basis, a total sample size of 394 participants under equal randomisation will provide 90% power (accounting for 10% drop out rate) to detect a change of 1 from baseline on the mJOA scale (assuming a standard deviation [SD] of 2.89), using a two-sided t-test at a 5% significance level.

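### The covariate list in 15.1 leaves out baseline mJOA, a stratification factor, so the BPI, NDI, SF-36 PCS and SF-36 MCS comparisons are not adjusted for it: a minor, conservative loss of precision

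*Protocol*

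**What the plan says.** On randomisation, protocol section 9.3 states: "Stratified blocked randomisation will be used stratifying by baseline mJOA (<12 vs >=12), age (<60 years vs >=60 years) and time to onset", the last factor being split at six months. Allocation is 1:1 in blocks of random size.

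On adjustment, section 15.1 states: "The following baseline covariates, in addition to the baseline value of the endpoint, will be used to adjust all comparisons". The five named covariates are time to onset, smoking status, age, psychiatric comorbidities and impaired gait.

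On the endpoints concerned, section 15.1 introduces a ranked list: "The ordering of subsequent endpoints for formal hypothesis testing will be". The order is BPI pain, NDI, SF-36 PCS, SF-36 MCS, mJOA upper-limb motor score and mJOA lower-limb motor score. The same section says the trial is not powered for a specific difference on these and that the analysis will estimate the difference. It also promises a detailed SAP before final database lock; that SAP is not available here.

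**The concern.** Stratifying by a prognostic factor makes the arms alike on that factor, so the treatment estimate varies less from one randomisation to another. An analysis that leaves the factor out does not know this. It leaves the between-stratum variation in the residual error, reports a standard error that is too large, and tests below its nominal level.

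Two of the three stratification factors are in the list and the third is not. For the total mJOA the gap closes itself, because the endpoint's own baseline is the missing factor. For the first four ranked secondary endpoints it does not. These are the comparisons for which the protocol's stated aim is estimation, so confidence intervals that are too wide bear on that aim directly.

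**Working it through.** **1. Which stratification factors reach which model.** Setting 9.3 against the rule in 15.1:

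| Endpoint | Age | Time to onset | Baseline mJOA |
|---|---|---|---|
| mJOA total (if adjusted by the 15.1 rule) | listed | listed | yes, as own baseline |
| BPI, NDI, SF-36 PCS, SF-36 MCS | listed | listed | absent |
| mJOA upper- and lower-limb motor scores | listed | listed | in part, through the baseline sub-score |

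No other section of the protocol adds the stratification factors as covariates.

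**2. The plan's own figure.** Section 15.3 uses a difference of 1 point, SD 2.89, two-sided 5%, 90% power and 10% drop-out. The normal approximation gives 2 × (1.960 + 1.282)² × 2.89² / 1² = 175.5, so 176 per arm, 352 in total, and 352 / 0.9 = 391.1, or 392. The exact t calculation gives 177 per arm, 354 in total, and 354 / 0.9 = 393.3, or 394 as an even number. The stated 394 is reproduced, and nothing below changes it.

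**3. Effect of the omission.** The protocol gives no correlation between mJOA and these scales, so r is an assumption. It is the correlation between the mJOA stratum and the 24-month endpoint after the endpoint's own baseline and the five listed covariates. Let k = √(1 − r²). Under stratified randomisation the true standard deviation of the estimate is k times the standard error that the model without the stratum reports. Therefore:

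- excess of the reported standard error = 1/k − 1
- actual level of the nominal 5% test = 2 × [1 − Φ(1.96/k)]
- power with the stratum, when power without it is 80% (z = 0.842) = Φ(0.842 + 1.96 × (1/k − 1))

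| r | k | SE too wide by | Actual level | Power with stratum | Gain (points) |
|---|---|---|---|---|---|
| 0.2 | 0.980 | 2.1% | 4.55% | 81.1% | 1.1 |
| 0.3 | 0.954 | 4.8% | 3.99% | 82.5% | 2.5 |
| 0.4 | 0.917 | 9.1% | 3.25% | 84.6% | 4.6 |
| 0.5 | 0.866 | 15.5% | 2.36% | 87.4% | 7.4 |

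Worked line for r = 0.5: 1/k = 1.1547; 1.96 × 0.1547 = 0.303; 0.842 + 0.303 = 1.145; Φ(1.145) = 0.874.

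The 80% base is also an assumption, since the protocol states no SD or power for these scales.

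**4. Check by simulation.** Stratified blocked randomisation of 354 patients was simulated with 6,000 runs per setting, 40% of patients assumed to have mJOA below 12, and a linear model fitted without and with the stratum. The standardised difference for power was 1/2.89.

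| r | Type I error, without / with | Power, without / with |
|---|---|---|
| 0 | 5.1% / 5.1% | 90.3% / 90.3% |
| 0.2 | 4.8% / 5.3% | 90.1% / 91.1% |
| 0.3 | 3.7% / 4.6% | 90.7% / 92.1% |
| 0.4 | 3.4% / 5.0% | 91.8% / 94.4% |
| 0.5 | 2.4% / 5.0% | 92.8% / 96.4% |

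Monte Carlo error on the type I figures is about 0.3 points. Mean standard errors without the stratum were about 2% larger at r = 0.2 and about 16% larger at r = 0.5, in line with the formula. The power gains are smaller than in step 3 because the base is about 90%.

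**The case against.** The strongest reply is that little depends on this. The error is conservative and confined to secondary endpoints that the protocol says it is not powered for. The r needed for a material effect is also demanding, because it is what remains after the endpoint's own baseline and five covariates. One of these, impaired gait, overlaps the lower-limb part of the mJOA. The first-ranked endpoint is pain, which section 8.6.1 says the mJOA reflects only to a limited degree. All of this stands, and it limits the weight of the point.

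A second reply is that the list does not claim to be exhaustive and the SAP could add the missing factor. This carries less weight. The protocol names the covariates for every comparison, so an SAP that follows it literally repeats the gap.

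Three stronger readings are tempting, and the documents do not support them.

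- A reader might infer that the omission biases the estimates or inflates false positives. It does neither; the actual level falls below 5%.
- A reader might compute the power loss as if adding the term cut the true variance of the estimate by r². At an 80% base that gives 1.6, 3.6, 6.4 and 9.9 points for r = 0.2 to 0.5. It overstates the cost, because stratification has already removed the stratum's share from the true variance and only the reported standard error is wrong.
- A reader might infer that a miss on BPI would stop all later tests and so multiply the loss. Section 15.1 gives an order for formal testing but does not say what follows a non-significant result.

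**Conclusion.** The point holds as a minor one. Read literally, 15.1 adjusts four ranked secondary endpoints for two of the three stratification factors, and two more for the third only in part. If the stratum is prognostic given the other covariates, standard errors are too wide and the tests conservative. The loss is small at r of 0.2 or below (about 1 point of power at an 80% base) and reaches 4.6 to 7.4 points only at r of 0.4 to 0.5, values that nothing in the protocol supports or excludes.

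The sample size is unaffected. So is the mJOA comparison, provided it is adjusted for its own baseline as 15.1 requires. The same section also says of the primary objective: "The primary objective will be evaluated using a two-sided t-test at a 5% significance level". How that fits with the adjustment rule is a separate question and is not decided here.

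**What to change.** In 15.1, add to the covariates for all comparisons: baseline mJOA (the pre-randomisation screening value used for stratification). Every ranked secondary endpoint is then adjusted for all three stratification factors as well as its own baseline value, and the SAP should repeat the list.

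Naming the screening value matters. Sections 11.3.2 and 11.6 place randomisation after screening and before the pre-operative baseline assessment, and mJOA is recorded at both, so the screening value is the one available to define the stratum.

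The cost is about one degree of freedom out of roughly 354 evaluable patients (394 × 0.9 = 354.6). No new data are needed and the sample size does not change.
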